1. INTRODUCTION

Purpose of statistical analysis plan

The purpose of this document is to provide details of the statistical analyses and presentation of results to be reported within the principal paper(s) of the EPOCH trial. Subsequent papers of a more exploratory nature will not be bound by this strategy but will be expected to follow the broad principles laid down within it. Any exploratory, post-hoc or unplanned analyses will be clearly identified as such in the respective study analysis report.

This document has been developed prior to examination of unblinded trial data. This plan is intended not to change or contradict the general aims of the protocol, but rather expand on them. In the event of a discrepancy the analyses described here will supersede those in earlier documents.

Background

EPOCH is a stepped wedge, cluster randomised trial which aims to evaluate the effect of a quality improvement intervention to promote the implementation of an integrated peri-operative care pathway in patients undergoing emergency laparotomy. The trial will take place in 90 hospitals, which have been grouped into 15 clusters based on geographical location (with approximately 6 hospitals per cluster). The trial will take place over an 85 week period, which has been divided into 17 time periods of 5 week each. All hospitals will start out receiving usual care during the first time period; during each subsequent time period, one cluster will switch over to the quality improvement intervention (the order the clusters switch has been randomised). By time period 16, all clusters will be receiving the quality improvement intervention.

Inclusions/exclusion criteria

Inclusion criteria

- Included on the NELA database
- Age 40 years and over
- Undergoing non-elective surgery
- Undergoing open abdominal surgery
- Admitted to hospital during the 85 week trial period from March 3rd 2014, to Oct 19th, 2015

Exclusion criteria

- Patients who have previously been included in the EPOCH trial •
- Laparotomy to treat complications of recent elective surgery
- Simple appendicectomy
- Gynaecological laparotomy
- Surgery related to organ transplant
- Laparotomy for traumatic injury

Changes from protocol

- Defined the process measures to be summarised
- Defined which baseline risk factors were to be adjusted for in the analysis
- Clarified that hospitals which discontinue their emergency laparotomy service, or which merge with another hospital during the trial period will be excluded from the analysis at the point of discontinuation or merger
- Clarified that the analysis will include a random-effect for the hospital-time period interaction. This is in accordance with new research indicating this analysis approach is required to preserve type I error rates at their nominal level
- Clarified that hospital re-admission will be analysed using a competing-risk time-to-event model rather than a logistic regression model
- Clarified that time to hospital discharge will be analysed using a competing-risk time-to event model rather than a simple time-to-event model

Note that all changes from the protocol were made before any investigators had access to any trial data or to any results.

Changes from SAP version 1.0

• Changed the covariates to be adjusted for in the analysis of clinical outcomes from age and gender, to age, gender, and indication for surgery.

Note that all changes from version 1.0 of the SAP were made before any investigators had access to any clinical outcome data.

Changes from SAP version 2.0

We had planned to calculate the primary outcome (mortality within 90 days of surgery) based on data obtained from government registries (i.e. Office for National Statistics in England, and similar agencies in Scotland and Wales), and analyse it as a binary endpoint using a logistic regression model. However, due to unforeseen issues, we were unable to obtain data from the Welsh registry (but did obtain data from the English and Scottish registries). This meant that under our original definition, all patients in Wales would be excluded from the analysis due to missing data, which could adversely affect results. In order to avoid excluding patients from Wales from the primary outcome analysis, we opted to change the analysis approach from a logistic regression model based on a binary endpoint to a survival analysis model based on a time-to-event endpoint; this allowed us to calculate time-to-mortality for patients in Wales

based on in-hospital mortality data which is collected as part of NELA (with patients being censored at the time of hospital discharge). Time-to-mortality will still be calculated based on government registry data for patients in England and Scotland. We changed the secondary outcome 'mortality within 180 days' in the same manner. The updated method for deriving these outcomes is available in Appendix 3.

- One of the sensitivity analyses regarding missing data for the primary outcome was based upon a binary endpoint; this has been removed, as this approach does not work well for time-to-event outcomes.
- Removed sensitivity analysis for primary outcome which included patients who presented to a hospital which merged with other hospitals after the date of the merge, as this affected very few patients.
- Added specification that missing data in the baseline covariates that will be adjusted for in the analysis will be handled using mean imputation (for continuous variables) and a missing indicator variable (for categorical variables).
- Appendix 5: Updated to reflect new data fields in NELA, and a 'multiple indications' category was added as the categories are not mutually exclusive.
- Clarified that the additional analysis assessing the intervention in patients aged <40, or who
 underwent laparoscopic surgery would not be a formal analysis, but would only present
 summary statistics. This is because we expect few patients and outcome events in this group,
 and our specified statistical models (with three levels of random-effects) would likely not work
 well.
- Appendix 2: clarified that patients who presented to a hospital that merged with other hospitals after the date of the merge would be excluded from the analysis (this was stated in v2.0 of the SAP, but inadvertently left out from the appendix)

Changes from version 2.0 of the SAP were after the trial statistician (BK) had access to data, but before statistical analysis began (i.e. during the data cleaning stage), and before any other investigators had access to the data.

2. OUTCOME MEASURES

Primary outcome

All-cause mortality within 90 days following surgery

Secondary outcomes

- All-cause mortality within 180 days following surgery
- Duration of hospital stay (defined as the number of days from surgery until hospital discharge)
- Hospital re-admission within 180 days of surgery

The start of surgery will be defined as when the patient enters the operating theatre or anaesthetic room.

Process measures

- 1. Consultant led decision to operate
- 2. When consultant led decision to operate, did this consultant personally review patient at time of decision?
- 3. Preoperative documentation of risk
- 4. Time from decision made to operate to entry into operating theatre
- 5. Patient entered operating theatre within time-frame specified based on their urgency level (i.e. <2 hours, 2-6 hours, 6-18 hours, or >18 hours)
- 6. Consultant surgeon present in operating theatre
- 7. Consultant anaesthetist present in operating theatre
- 8. Goal directed fluid therapy used during surgery
- 9. Arterial lactate measured at end of surgery
- 10. Critical care admission immediately after surgery

3. STUDY METHODS

Overall study design and plan

Multi-centre, stepped wedge cluster randomised trial conducted in 90 NHS hospitals over an 85 week period, divided into 17 time period of 5 weeks. Hospitals will be grouped into fifteen clusters of six on a geographical basis. The quality improvement intervention will commence in one geographical area each five week step from the 2nd to the 16th time period, with the order of geographical areas determined by computer based randomisation.

Randomisation

Simple randomisation was used to randomise one geographical area of hospitals to receive the intervention in each of the fifteen time periods 2 to 16. Randomisation was performed by an independent statistician. Local investigators were notified 12 weeks in advance of activation of the quality improvement project at their hospital.

Sample size

Prospectively collected data from the recently published Emergency Laparotomy Network study in 35 NHS hospitals closely match our inclusion/exclusion criteria and describe a median of 184 eligible patients aged \geq 40 years per hospital per year (range 32-736). Data from the Hospital Episodes Statistics database for the year ending April 2011 gives average 90-day mortality as 25%. These data have been used to estimate the baseline mortality rate and between hospital coefficient of variation. Power calculations are based on the methodology proposed by Hussey & Hughes, for an analysis with fixed time effects and random cluster effects, modified to exclude data collected during the five week period in which the intervention commences in individual hospitals. The trial will be conducted in at least 90 NHS hospitals over a period of 85 weeks during which time we expect to receive data describing 27,540 patients undergoing emergency laparotomy. For a baseline 90-day mortality of 25%, between hospital coefficient of variation of 0.15, constant case-load (18 patients per 5 weeks per hospital) and assuming independent hospital effects, the study would achieve 92% power to detect a 12% relative risk reduction in mortality from 25% to 22% (two-sided p<0.05). This calculation is insensitive to the coefficient of variation but sensitive to the effect size. In practice, power may be reduced by correlation between hospitals within geographic areas and by variation in case-load between hospitals. The worst case scenario is one where each of the 15 geographic areas functions effectively as a single large hospital, reducing the power to 83%. This figure incorporates an adjustment for variable case-load from the pilot data. Thus the power of the study to detect a 12% relative risk reduction lies between 83% and 92%.

4. DATA COLLECTION

Data to be collected at different stages:

Pre-operative data: Age, Sex, American Society of Anesthesiologists (ASA) Score, Co-morbid disease, Date of hospital admission, Admitting specialty, Time and date of decision to perform surgery, Time to diagnostic imaging (usually computed tomography scan of the abdomen), Documented mortality risk before surgery (Y/N).

Intra-operative data: Urgency of surgery, Duration, time and date of surgery, Grades of most senior surgeon and anaesthetist present in theatre, Surgical procedure performed, Underlying pathology.

180-day follow-up: Critical care admission, Duration of hospital stay, Hospital readmission and mortality.

5. ANALYSIS PRINCIPLES

Patients and hospitals to be included in the analysis

All analyses will be conducted on an intention-to-treat basis. All eligible patients with available outcome data who attended a participating hospital during the 85-week trial period will be included in the analysis. Patients who presented to hospital during the 5-week time period immediately after the quality improvement implementation will be excluded from the analysis, in order to allow time for the intervention to take effect.

Hospitals that underwent randomisation but subsequently withdrew prior to the trial start date (March 3rd, 2014) will be excluded from the analysis. Hospitals that withdraw from the trial during the trial period or do not implement the intervention will be included in the analysis. Hospitals that discontinue their emergency laparotomy service during the trial period will be included in the analysis up until the point of discontinuation, and excluded after this point. Hospitals that merge with another hospital(s) during the trial period will be included in the analysis up until the point of the withdraw from data collection during the trial period will be included in the analysis up until the analysis up until the point. Hospitals that withdraw from data collection during the trial period will be included in the analysis up until the analysis up until the point. Patients will be considered exposed to the intervention based on the randomisation schedule, regardless of whether the intervention was actually implemented.

Justification for excluding hospitals who merge with other hospitals during the trial period

When hospitals merge they can be seen to form a 'new' hospital. The types of patients who present to the new hospital may be different to those that presented to the 'original' hospital (e.g. due to a wider or different catchment area). There may be differences in staff between the new and original hospitals (e.g. differences in doctors, surgeons, nurses, etc). In some cases there may be differences in available equipment. This could all lead to substantial differences between the pre- and post-merger outcomes for patients. Because the stepped-wedge trial relies heavily on a within-hospital comparison, differences between pre- and post-merger outcomes could substantially skew this comparison, which could lead to bias in the estimated treatment effect.

General analysis principles

For analysis of the primary and secondary outcomes, the following summaries will be provided:

- The number of patients included in the analysis, by treatment group
- The number of hospitals included in the analysis
- A summary statistic for the outcome (e.g. the number (%) of patients experiencing an event for binary outcomes)
- The estimated treatment effect with its 95% confidence interval and a two-sided p-value

The significance level is set at 5%. All analyses will include time-period in the model as a fixed-effect using indicator variables. All analyses will adjust for age, gender, and indication for surgery (peritonitis, perforation, abdominal infection, intestinal obstruction, haemorrhage, ischaemia, other, or multiple indications) using fixed factors. Age will be included as a continuous covariate, and will be assumed to have a linear association with the outcome. Missing baseline data will be imputed using mean imputation for continuous variables (age), and using a missing indicator for categorical variables (gender, indication for surgery) (based on guidance from White IR, Thompsons SG. *Adjusting for partially missing baseline measurements in randomized trials.* Stat Med 2005).

Primary outcome

The primary outcome (all-cause mortality up to 90 days following surgery) will be analysed using a mixed-effects parametric survival model, with a Weibull survival distribution. This model will include random-intercepts for geographical area, hospital, and the interaction between hospital and time-period. Time-period will be included in the model as a fixed-effect using indicator variables. Age, gender, and indication for surgery will also be included in the model as fixed factors.

Note that we are including the interaction between hospital and time-period as a random-effect as recent research has indicated this is required in order to preserve type I error rates at the nominal level (i.e. Morgan K, Forbes A, Keogh R, Jairath V, Kahan B. *Choosing appropriate analysis methods for cluster randomised cross-over trials with a binary outcome.* Accepted.)

An example dummy dataset is provided in table 1 and example Stata code is provided below to demonstrate how this analysis will be implemented.

Example Stata code

stset time_to_outcome, failure(outcome)

mestreg treatment i.time_period age gender i.indication_surgery || geo_area: || hospital: || hospital_time_period: , distribution(weibull)

If there are convergence issues with this analysis approach, we will use the strategy shown in table 2 to find an analysis approach which converges.

Table 1 – Example dataset

| Geographical | Hospital | Time period | Hospital*time | Treatment | Patient |
|--------------|----------|-------------|--------------------|-----------|---------|
| area | | | period interaction | | |
| 1 | 1 | 1 | 1 | 0 | 1 |
| 1 | 1 | 1 | 1 | 0 | 2 |
| 1 | 1 | 2 | 2 | 0 | 3 |
| 1 | 1 | 2 | 2 | 0 | 4 |
| 1 | 2 | 1 | 3 | 0 | 5 |
| 1 | 2 | 1 | 3 | 0 | 6 |
| 1 | 2 | 2 | 4 | 0 | 7 |
| 1 | 2 | 2 | 4 | 0 | 8 |
| 2 | 3 | 1 | 5 | 0 | 9 |
| 2 | 3 | 1 | 5 | 0 | 10 |
| 2 | 3 | 2 | 6 | 1 | 11 |
| 2 | 3 | 2 | 6 | 1 | 12 |
| 2 | 4 | 1 | 7 | 0 | 13 |
| 2 | 4 | 1 | 7 | 0 | 14 |
| 2 | 4 | 2 | 8 | 1 | 15 |
| 2 | 4 | 2 | 8 | 1 | 16 |

Table 2 – Analysis approaches to be used if the primary method of analysis fails to reach convergence

| | Change from previous strategy | Example Stata code |
|---|--|---|
| 1 | Remove the random-effect for the hospital/time-period interaction | mestreg outcome treatment i.time_period age gender i.indication_surgery geo_area: hospital: , distribution(weibull) |
| 2 | Remove the random-effect for hospital | mestreg outcome treatment i.time_period age gender i.indication_surgery geo_area: , distribution(weibull) |
| 3 | Adjust for the fixed-effect of time as a continuous covariate using restricted cubic splines with 7 knot points (where rcs_time_period* are the variables forming the restricted cubic spline) | mestreg outcome treatment rcs_time_period* age gender i.indication_surgery geo_area: , distribution(weibull) |

Secondary outcomes

All-cause mortality up to 180 days

All-cause mortality up to 180 days following surgery and hospital re-admission within 180 days of surgery will be analysed using the same approach as the primary outcome.

Duration of hospital stay

Duration of hospital stay will be analysed using a competing-risk time-to-event model, which recognises mortality as a competing risk for hospital discharge. Because there are no facilities for analysing competing risk data using mixed-effects models in Stata, we will use robust standard errors which account for clustering by geographical area. This analysis will be implemented in Stata as follows:

stset cc_time_to_discharge, failure(cc_discharge == 1)

stcrreg treatment i.time_period age gender i.indication_surgery, compete(cc_discharge == 2) vce(cluster geo_area)

Where:

cc_discharge is a variable indicating whether the patient was discharged home (=1), died in hospital (=2), or was censored (=0), and *cc_time_to_discharge* is a variable indicating the time to the event.

Hospital re-admission within 180 days

This outcome will be analysed using a competing-risk time-to-event model, which recognizes mortality as a competing risk for hospital re-admission. It will be implemented using the same code as *duration of hospital stay* above.

Secondary analyses of the primary outcome

Evaluating the effect of the intervention over time

We will perform a secondary analysis of the primary outcome to evaluate the effect of the intervention over time (i.e. whether the intervention effect improves over time). This analysis will include patients who presented to hospital during the 5-week period immediately after implementation of the quality improvement intervention. We will evaluate the following four groups:

- Usual care;
- The quality improvement (QI) intervention implemented for less than 5 weeks
- The QI intervention was implemented for 5 weeks or more and less than 10 weeks
- The QI intervention was implemented for 10 weeks or more

This analysis will allow us to determine whether the effectiveness of the QI intervention improves over time. The analysis will be implemented using the same method as for the primary analysis of the primary outcome.

Inclusion of other patient populations which may be affected by the intervention

We will perform a sensitivity analysis to assess whether results are generalisable to other patient populations which may have been affected by the intervention. This includes patients who underwent laparoscopic surgery, and patients who are aged 18-40 years.

Due to the small number of patients in these groups, we will summarise results descriptively, rather than undertaking a formal statistical analysis. We will summarise the number (%) of patients in the treatment arms who experience a primary outcome event. The denominator for this analysis will include patients who either underwent laparoscopic surgery or were aged 18-40 years (or both), and who met all other eligibility criteria.

Process measures

The process measures will be summarized according to treatment group. For example, for binary process measures (e.g. 'Goal directed fluid therapy used during surgery'), the number (%) of patients for whom the measure was met will be summarised separately for patients presenting during the usual care period and patients presenting during the intervention period.

Because the trial intervention is complex, and we will not be able to distinguish the effects of a change in any one process measure on patient outcomes, no formal statistical analysis will be performed. This is to avoid any misinterpretation that changes in some process measures affected patient outcomes whilst others did not.

Graphs and other data summaries

Survival curves for mortality up to 180 days from surgery

We will present two graphs which display the survival curves for mortality up to 180 days after surgery. Survival curves will be presented for each treatment arm. The first graph will be a Kaplan-Meier plot. It should be noted that this plot is affected by overall time trends in the outcome (e.g. if mortality rates improved over time, regardless of the intervention).

Therefore, the second graph will show the estimated survival curve based on a mixed-effects time-toevent model, which corrects for time trends. The Stata code to implement this graph is:

stset time_to_death, failure(died_180days)

mestreg treatment i.time_period age gender i.indication_surgery || geo_area: || hospital: || hospital_time_period: , distribution(Weibull)

stcurve, surv at1(treatment=0) at2(treatment=1)

Other data summaries

- The number of patients who are excluded from each analysis (and the reasons why) will be summarized.
- The number of cluster activation meetings that occurred within ±2 weeks of the date based on the randomisation list
- The number of hospitals sending at least one person to the first QI activation meeting
- The number of hospitals sending at least one of their named QI leads to the first QI activation meeting
- The number of hospitals sending at least one person to the second QI activation meeting
- The number of hospitals sending at least one of their named QI leads to the second QI activation
 meeting

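### Areas are randomised to steps, but the mortality models have no area-by-period random effect, so intervals may be too narrow and 83% power is not a lower bound

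*SAP*

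**What the plan says.** - **Unit of randomisation** (SAP section 3, Randomisation). The plan states: "Simple randomisation was used to randomise one geographical area of hospitals to receive the intervention in each of the fifteen time periods 2 to 16". The design paragraph adds: "Hospitals will be grouped into fifteen clusters of six on a geographical basis". Section 5 classifies exposure by the randomisation schedule, so hospitals in one area change treatment status together.
- **Primary model** (section 5, Primary outcome): "This model will include random-intercepts for geographical area, hospital, and the interaction between hospital and time-period". The Stata code and example dataset show the same structure. The reason given for the hospital-by-period term is that "recent research has indicated this is required in order to preserve type I error rates at the nominal level". All-cause mortality to 180 days is analysed in the same way.
- **Fallbacks** (section 5, Table 2): the first step on non-convergence drops hospital-by-period, the second drops hospital, and the third replaces the period indicators with splines. After the first step no random effect varies by period.
- **Robust errors** (section 5, Secondary outcomes): standard errors clustered on area are planned for length of stay and re-admission, not for mortality.
- **Power** (section 3, Sample size): a Hussey & Hughes calculation with fixed time effects and random cluster effects gives 92% for independent hospitals. For the lower end: "The worst case scenario is one where each of the 15 geographic areas functions effectively as a single large hospital". That gives 83%, including an adjustment for variable case-load. Power is then said to lie between these two figures.

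**The concern.** Treatment is constant within an area-period. A period-specific deviation shared by the hospitals of one area, such as a regional staffing or winter-pressure effect, is therefore aligned with the treatment indicator. The fixed period effects remove only what is common to all areas. The SAP's model lets hospitals in an area share a permanent level but treats their period-specific deviations as independent. A shared deviation is then averaged over six hospitals as if it were six separate ones.

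The SAP accepts that a cluster-by-period term is needed to hold the type I error, and that an area may behave like one large hospital. Taken together, these point to a term at area level. The primary confidence interval and p-value are at stake, in the anti-conservative direction. So is the lower end of the power range, which assumes area effects perfectly stable over 85 weeks.

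**Working it through.** **Inputs from the SAP (section 3, Sample size):** mortality 25% against 22%, two-sided 5%, and "between hospital coefficient of variation of 0.15, constant case-load (18 patients per 5 weeks per hospital) and assuming independent hospital effects". There are 90 hospitals, 15 areas and 17 periods, with the transition period dropped.

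**Derived:** τ = 0.15 × 0.25 = 0.0375, so τ² = 0.00140625. Patient-level variance = 0.25 × 0.75 = 0.1875. Variance of a hospital-period mean: s² = 0.1875/18 = 0.010417. Variance of an area-period mean: 0.1875/108 = 0.001736.

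**Assumed:** total between-cluster variance stays at τ², and a share (1 − CAC) of it varies by period. The SAP gives neither a CAC nor the share of variance at area level. All figures use a linear model on the risk scale, not the Weibull model.

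**Step 1. The plan's power figures.** Var(θ) is the treatment element of (X′V⁻¹X)⁻¹ with fixed period effects, and power = Φ(0.03/SE − 1.96).
- 90 independent hospitals: SE 0.00885, and 0.03/0.00885 − 1.96 = 1.43, so power is 92.3%. The stated 92% reproduces.
- 15 areas of 108 patients per period: SE 0.00970, and 0.03/0.00970 − 1.96 = 1.13, so power is 87.1% before any case-load adjustment.
- Going from 87.1% to 83% needs a variance inflation of about 1.125, or 108/1.125 = 96 effective patients per area-period. The SAP does not give the adjustment, so 83% can be neither reproduced nor refuted.

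**Step 2. Power of the 15-area worst case with area-by-period variance added.** The calibrated column uses 95 effective patients per area-period.

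| CAC | Calibrated to about 83% | No case-load adjustment |
|---|---|---|
| 1 | 82.9% | 87.1% |
| 0.95 | 81.8% | 86.0% |
| 0.9 | 80.7% | 84.8% |
| 0.8 | 78.7% | 82.7% |
| 0.7 | 76.9% | 80.7% |

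**Step 3. Standard error of the SAP's model.** Area + hospital + hospital-by-period was fitted (expected REML) to a truth that includes area-by-period variance. The ratio is the model SE over the true (sandwich) SE, and type I error = 2[1 − Φ(1.96 × ratio)].

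| Share of variance at area level | CAC 1 | CAC 0.9 | CAC 0.8 | CAC 0.7 |
|---|---|---|---|---|
| 25% | 1.000 (5.0%) | 0.993 (5.2%) | 0.986 (5.3%) | 0.980 (5.5%) |
| 50% | 1.000 (5.0%) | 0.985 (5.4%) | 0.972 (5.7%) | 0.959 (6.0%) |
| 100% | 1.000 (5.0%) | 0.969 (5.8%) | 0.943 (6.5%) | 0.920 (7.1%) |

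**Hand check of one cell (100%, CAC 0.9).** With d = 0.1 × 0.00140625 = 0.000141, the true area-period variance is s²/6 + d = 0.001877. The model implies (s² + d)/6 = 0.001760. The ratio is 1.067, so the model SE is 1/√1.067 = 0.968 of the true SE and the type I error is about 5.8%. This agrees with the table.

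**The case against.** The strongest reply is that the harm is conditional and small. The period indicators already absorb all common time trends, and the SAP gives no evidence that areas drift apart from them. Its type I error argument concerns hospital-by-period variation, so carrying it up to area level is an inference. The coefficient of variation of 0.15 is a between-hospital figure, paired in the SAP with independent hospitals, so placing all of it at area level is an upper case. With half of it there, the correctly specified model has 87.2%, 86.3% and 85.5% power at CAC 0.9, 0.8 and 0.7 before case-load adjustment, which is inside the stated range. Measured from the unadjusted 87.1%, even the 15-area case goes below 83% only at a CAC of about 0.8 or lower. The shared activation meetings do not help the concern: they occur at the switch and would produce shared intervention effects, not the shocks under the null that inflate type I error.

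Most of this stands and limits the size of the point. It does not remove it. The term is absent at the level where treatment was assigned, no robust error or sensitivity analysis covers mortality, and any positive area-by-period variance acts in the anti-conservative direction.

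A reader might infer that the standard error is certainly too small. The documents do not support that, because the error is nil if area-by-period variance is zero. A reader might also take a more extreme case. With CAC 0.5 and all drift at area level, the hand formula gives a type I error of about 8.8% and the calibrated power is about 74%. Nothing in the SAP supports that combination.

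**Conclusion.** The point holds in conditional form. Both mortality models lack a random effect for area by period although area is the randomised unit. If areas vary by period beyond the common effects, at an assumed CAC of 0.9 to 0.7, the standard error is about 1-8% too small and the type I error about 5.2-7.1%, depending on the share of variance at area level.

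The 83% is not a worst case, because it assumes no cluster-by-period variance. Calibrated to about 83% at CAC 1, it falls to about 82-77% at CAC 0.95 to 0.7. The fall is less certain than the direction, because the case-load adjustment is not shown. It would be wrong to conclude that the 83% is an arithmetical error.

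The figures rest on a linear approximation and on CAC values that are the review's assumptions. This is a correction that should be made, not one on which the trial's validity turns.

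**What to change.** 1. **Models.** Add a geographical area-by-time-period random intercept to the 90-day and 180-day mortality models, keeping hospital-by-period. In Stata this could be a `geo_area: R.time_period` term with a Laplace fit.
2. **Table 2.** Keep the area-by-period term when hospital-by-period and then hospital are dropped, and in the spline step. Once hospital is dropped, area-period is simply nested in area. If the term cannot be fitted, use area-level robust inference with a small-sample correction for 15 areas. Alternatively, use a permutation test of the model's treatment coefficient over the allocation of areas to steps.
3. **Sample size section.** Describe 83% as conditional on no area-by-period variation. Delete the claim that power lies between 83% and 92%, or show power over a CAC range labelled as an assumption.

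**Cost.** The fit has crossed effects (hospital with area-period), so run time is longer and there is some convergence risk. The confidence interval would be slightly wider and the power statement slightly less favourable. The sample size is unaffected. If the area-by-period variance is near zero, the extra term costs almost nothing in precision.
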